Official Title: Carotid Plaque Composition by Magnetic Resonance Imaging During Lipid Lowering Therapy

NCT00715273

Study Protocol and Statistical Analysis Plan - 06APR2016

This final protocol version reflects the extension of clinical events monitoring and open-label study as supported by American Heart Association and Alpha Phi grants.

Responsible Party:

Principal Investigator

[name] [[name]]

Professor

University of Washington, Seattle, WA, USA

Study Protocol and Procedures (April 2016)

Study Title: CAROTID PLAQUE COMPOSITION BY MRI DURING LIPID-
LOWERING, supported by NHLBI (R01 HLO63895)

Short title: CPC

A. Study Protocol

A.1. Study Objectives/Aims:

(1) To test the primary hypothesis that intensive lipid therapy decreases carotid plaque lipid content assessed by CE-MRI. To achieve this goal, we will (a) perform carotid CE-MRI scans for all 180 study subjects at baseline, 1, 2, and 3 years; (b) perform quantitative assessments of plaque lipid content; (c) compare the plaque lipid content between pre- and post-treatment for all 3 therapy groups; (d) demonstrate the time-course of plaque lipid content change during intensive lipid modification over 3 years by assessing serial carotid CE-MRI examinations.

(2) To test the secondary and exploratory hypotheses that intensive lipid therapy is associated with plaque regression and decreased plaque enhancement assessed by CE-MRI. To achieve this goal, we will (a) perform quantitative assessments of plaque volume and enhancement; (b) compare the plaque volume and enhancement between pre- and post-treatment for all 3 therapy groups; (c) examine the relationship between plaque lipid and volume and enhancement characteristics; (d) demonstrate the time-course of plaque volume and enhancement change during intensive lipid modification over 3 years.

(3) To examine the association of factors including clinical risk factors, lipids, lipoprotein heterogeneity, inflammatory markers, oxidative stress markers and carotid plaque characteristics (lipid, volume, and enhancement). To achieve this goal, we will (a) perform laboratory testing on lipids, lipoprotein heterogeneity, inflammatory markers, oxidative stress markers at baseline and on therapy; (b) describe the change in each of these measurements between baseline and on treatment; (c) determine the statistical significance of each measured risk variable and its change in relation to the change in plaque characteristics.

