(4) To investigate the effects of HDL-raising and very intensive LDL-lowering on carotid plaque characteristics over 3 years. To achieve this goal, we will (a) perform quantitative assessment of plaque lipid, volume, and enhancement at all 4 time points blinded to the MRI time sequence and treatment; (b) compare the change in plaque characteristics over 3 years between single and double therapy for HDL-raising effect, between double and triple therapy for more intensive LDL-lowering effect, and single and triple therapy for more LDL-lowering plus HDL-raising effect.

(5) To determine if carotid plaque characteristics predict future major cardiovascular events. To achieve this goal, we will (a) continue to conduct clinical follow-up for a median of 5 years to collect cardiovascular events including fatal/non-fatal MI or stroke, hospitalization/revascularization for worsening ischemia, and mortality; (b) determine whether plaque characteristics (lipid content, volume and enhancement) at baseline and its change during therapy are statistically associated with cardiovascular events.

[figure not shown]
This study employs the state-of-the-art technique to assess both the magnitude and mechanisms of benefit of lipid therapy. It will be one of the first studies to examine the effects of lipid-lowering therapy on human atherosclerotic plaques in vivo and will provide novel insights into our understanding of atherosclerotic plaque pathology and the mechanisms of lipid-lowering therapy preventing ischemic events.

A.2. Study Design:

This project is a randomized open-label study.

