In this research project we will perform carotid MRI studies in 180 CAD patients with a family history of cardiovascular disease and ApoB ≥ 120 mg/dl (LDL-C levels 100-190 mg/dl). Fifty percent of these subjects will be women. The qualified subjects will be randomized to one of three treatment groups: (1) single therapy - atorvastatin alone; (2) double therapy – atorvastatin plus Niacin (2 g/day); (3) triple therapy – atorvastatin, Niacin plus ezetimibe (10 mg/day). . The treatment target for LDL-C will be ≤ 80 mg/dl for the single and double therapy groups and ≤ 60 mg/dl for the triple therapy group. The HDL-C target for two niacin-treated groups will be 10-12 mg/dl increase. All patients will undergo MRI examination of both carotid arteries annually for three years, a total of 4 examinations. If subjects are enrolled in the trial extension a “late time” scan may be performed at a median time of six years.

Following figure illustrates the study design.

*If subjects are enrolled in the trial extension a “late time” scan may be performed at a median time of six years.

In order to determine if carotid plaque characteristics predict future major cardiovascular events, we will ask the study participants who have completed the original 3-year protocol and carotid MRI examinations to continue on their randomized therapy for up to 11 more years. We will (a) continue to conduct clinical follow-up during the extension to collect cardiovascular events including fatal/non-fatal MI or stroke, hospitalization/revascularization for worsening ischemia, and mortality; (b) determine whether plaque characteristics (lipid content, volume and enhancement) at baseline and its change during therapy are statistically associated with cardiovascular events.

Duration: a mean of 5 years and maximum of 11 years

A.3. Primary Efficacy Parameters:

Primary endpoint: The primary endpoint of this study is carotid plaque lipid composition identified by MRI. The determination of plaque lipid content for each carotid artery will be performed using the automated interactive system. These measurements will be performed from the MRI scans at four time points blinded to time sequence of MRI examinations, patient treatment, lipid levels and clinical course.

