3. Treatment effect with different lipid therapies: This set of analyses addresses the primary and secondary endpoints of determining the treatment effect on lipid composition, plaque wall volume and wall thickness. The simplest form of this analysis will be a t-test or nonparametric Mann-Whitney test comparing the two treatment groups on the change in an outcome variable between baseline and the 3-year MRI assessment. In order to control for important covariates, we will carry out multivariate linear regression, with the 3-year change in the outcome, such as percent of wall volume that is lipid-rich necrotic core, being the dependent variable and independent variables of treatment group (dichotomous). We will also evaluate baseline value of the outcome variable, and any other variables that need to be controlled, such as age and gender. We can also test for an interaction between variables in affecting the outcome by using an interaction term in the model. We will not automatically test all possible interactions. If main effects are included in a final regression model, it would be natural to test to see if there is an interaction between some of the main effects. Choice of which interactions to try will be driven by biological plausibility. For example, if treatment and baseline lipid composition are important and statistically significant main effects in a model, it would be natural to test to see if their interaction is also important. In general, quite large sample sizes are needed to detect interactions, unless they are very strong. However, the sign and magnitude and even marginal statistical significance of an interaction are informative, even if the interaction term is not ultimately included in the model. This comment on use of statistical interaction terms applies to the regression analyses for all of our aims. We routinely carry out statistical diagnostics on these analyses, such as examining residuals.

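### F.3 item 3 writes a two-group test and a two-level treatment term for a three-arm trial without saying how they map to the Aim 4 contrasts, and item 2 names logistic regression for a percentage outcome

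*Combined protocol and SAP*

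**What the plan says.** **Design.** Section A.2: "The qualified subjects will be randomized to one of three treatment groups", namely atorvastatin alone, atorvastatin with niacin, and both with ezetimibe. B.5 stratifies randomisation by gender, diabetes, smoking and triglycerides at or above 200 mg/dl.

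**Aims.** Aim 1: "To test the primary hypothesis that intensive lipid therapy decreases carotid plaque lipid content assessed by CE-MRI", assessed by comparing lipid content before and after treatment in all three groups. Aim 4 sets out the between-arm questions: "compare the change in plaque characteristics over 3 years between single and double therapy for HDL-raising effect", then "between double and triple therapy for more intensive LDL-lowering effect, and single and triple therapy for more LDL-lowering plus HDL-raising effect".

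**F.3 item 3 (treatment effect).** It opens: "This set of analyses addresses the primary and secondary endpoints of determining the treatment effect on lipid composition, plaque wall volume and wall thickness". Its simplest form is a t-test or Mann-Whitney test "comparing the two treatment groups on the change in an outcome variable between baseline and the 3-year MRI assessment". It then commits to linear regression with the 3-year change "being the dependent variable and independent variables of treatment group (dichotomous"). On covariates: "We will also evaluate baseline value of the outcome variable, and any other variables that need to be controlled, such as age and gender".

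**F.3 item 2 (baseline v 3 years).** It specifies paired t tests, then a logistic regression with plaque lipid composition as the dependent variable, meant to find patient or therapy variables that predict its change over 3 years. D.3, part 3(c), defines tissue composition as tissue volume over wall volume, expressed as a percentage.

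**The concern.** Item 3 never says which two groups are meant, whether any arms are combined, or whether the analysis is repeated for each Aim 4 pair. A two-level treatment term cannot by itself represent three arms, so an analyst must supply a step that the plan omits.

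The covariates are also open. The baseline value is something to evaluate rather than a fixed term. Of the four stratification factors only gender is named, and only as an example. In an open-label trial, the form of the treatment comparison and its adjustment set should be fixed before results by arm are seen. The blinding described in A.3 and D.3 covers image reading, not these choices.

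The inferential role of the Aim 4 contrasts is unclear as well. Aim 1 attaches the primary hypothesis to pre/post change, while item 3 says that its between-arm analyses address the primary and secondary endpoints. No order, allocation of significance level or overall test is given.

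In item 2, a logistic model needs a binary outcome or an explicit statement that a fractional response is being modelled. Neither is given, so the outcome and scale of that model are undetermined.

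**Working it through.** The plan gives no power or error figure for the between-arm comparison, so there is none to reproduce. Its only power statement (F.3 item 5) concerns correlations.

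**1. Side by side.**

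| Source | Groups or outcome |
|---|---|
| A.2, B.5 | three arms |
| Aim 4 | single v double, double v triple, single v triple |
| F.3 item 3, test | two groups, unnamed |
| F.3 item 3, regression | one dichotomous treatment term, outcome 3-year change, linear |
| F.3 item 2, model | lipid composition, logistic, target 3-year change |
| D.3, part 3(c) | composition is a percentage |

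**2. The readings of item 3 estimate different things.** Take a graded effect with arm means 0, 0.2575 and 0.515 SD, chosen for illustration. Run per pair, the contrasts are 0.2575, 0.2575 and 0.515 SD. With the niacin arms pooled against single therapy, the contrast is (0.2575 + 0.515)/2 = 0.386 SD, and double v triple is not estimated at all.

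The detectable difference at 80% power, two-sided 0.05, also differs. The formula is (1.960 + 0.842) × √(1/n₁ + 1/n₂):
- 60 v 60: 2.802 × √(2/60) = 0.51 SD
- 60 v 120: 2.802 × √(1/60 + 1/120) = 0.44 SD

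**3. Familywise error if the three contrasts were confirmatory.** Inputs:
- 180 completers (A.4, F.3 item 5).
- 60 per arm, an assumption. The text gives no ratio, and the design figure is not available to this review.
- Normal outcome, an assumption.
- Two-sided 0.05, stated only for the correlations and borrowed here.

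The three contrasts share arms. The chance that at least one is significant under the null is therefore P(Q > √2 × t) for the studentized range Q with 3 groups and 180 − 3 = 177 df, where t is the two-sided 5% critical value. The result is 0.122.

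Simulation with 200,000 trials per setting gives 0.121. It stays between 0.120 and 0.123 for 45 to 80 per arm and for 2:1:1, 1:1:2 and 1:2:2 splits of 180. Treating the tests as independent would overstate it: 1 − 0.95³ = 0.143.

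**4. Testing the arms overall first.** If the pairwise contrasts are tested only when the 2-df arm test is significant, simulated error under the global null is 0.050. With three arms this also holds when some arms differ, because then at most one of the three pairwise nulls can be true.

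Simulated power, 60 per arm, largest difference 0.515 SD:

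| Scenario | Contrast | Unadjusted | Overall test first |
|---|---|---|---|
| Graded effect | single v triple | 80% | 70% |
| Graded effect | each of the other two | 29% | 28% |
| Only triple differs | single v triple, double v triple | 80% | 76% |
| Only double differs | single v double | 80% | 76% |

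**5. Why the baseline term matters.** With equal variances at the two visits and correlation ρ between them, the residual variance is 2σ²(1 − ρ) for the unadjusted change and σ²(1 − ρ²) with baseline as a covariate. The ratio is (1 + ρ)/2, below 1 for any ρ below 1. The documents give no ρ, so the gain cannot be sized.

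**6. Degrees of freedom for a full model.** Arm 2 + baseline 1 + stratification factors 4 + age 1 + site 2 (three sites, A.5, as a fixed factor) = 10. With an intercept, 180 − 11 = 169 residual df.

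**The case against.** The strongest defence is that item 3 is a template applied once to each Aim 4 pair. Aim 4 names the pairs and gives each a purpose, and on that reading the t-test, the Mann-Whitney test and the dichotomous term all work. This largely stands. A reader might infer that the written analysis cannot be carried out in a three-arm trial. The documents do not support that: the problem is an unstated step, not an impossible analysis. What remains is that the template reading is nowhere stated and pooling fits the same words.

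A second defence is that Aim 1 and the paired tests in item 2 make pre/post change the primary hypothesis, while item 3's reference to primary and secondary endpoints may mean only that those variables are analysed by arm. That is the more natural reading. A reader might infer that the primary analysis carries a 12% error rate. It does not follow: the figure applies only if the Aim 4 contrasts are made confirmatory.

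Third, the t-test or Mann-Whitney alternative is not wholly unguided. Item 1 plans a check of distributions, and item 3 commits to regression with residual diagnostics. The missing selection rule is a detail.

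Fourth, a reader might note that item 3's outcomes differ from the secondary endpoints in A.3. Wall volume is computed from wall area (D.3), and Aim 2 already covers plaque volume, so what is left is an editorial point that adds no weight.

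Finally, item 3 should not be called the sole between-arm analysis of plaque lipid. Item 2 admits therapy variables as predictors, so it may be a second one, under a different model.

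**Conclusion.** The point holds as under-specification and inconsistency, and it should be fixed; it does not invalidate the trial. Three things rest on the text alone:
- The two-group wording is not mapped to three arms and three contrasts.
- The baseline and stratification covariates are not committed to.
- The logistic model in item 2 has no binary outcome, although item 3 uses linear regression for the same kind of outcome.

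The size, about 12% familywise error for one endpoint, is conditional. It needs the three contrasts to be treated as confirmatory and unadjusted, a normal outcome and two-sided 0.05 tests. It hardly moves across the arm sizes and splits examined. The effect sizes used for power are illustrations, since the plan states none for the treatment comparison.

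**What to change.** 1. **Item 3.** Make the main analysis one linear model of 3-year change with a three-level arm factor, the baseline value of the outcome, the four stratification factors, age, and the site/platform adjustment. F.3 item 1 describes a random site effect; if a fixed site factor replaces it, say so (2 df with three sites). Estimate the three Aim 4 contrasts with confidence intervals from this model. Keep the t-test and Mann-Whitney as supportive.
2. **Role.** Label the Aim 4 contrasts secondary to the Aim 1 pre/post hypothesis. If a between-arm claim is to be confirmatory, test the three contrasts only after a significant 2-df overall arm test.
3. **Item 2.** Replace the logistic regression with the linear model for 3-year change.

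**Cost.** Wording in the analysis section only; the covariates are already collected, and 169 residual df are ample. Labelling the contrasts secondary costs no power but gives up a confirmatory between-arm claim. Requiring the overall test first lowers single v triple power from 80% to about 70% under a graded effect, and power for the affected contrasts to about 76% when only one arm differs.

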4. Risk of cardiovascular events: This set of analyses will focus on the risk of CV events in relation to plaque characteristics and the changes over time in the plaque. We will use methods of survival analysis (failure-time analysis) for this part of the study. We will use Kaplan-Meier plots, the log rank test and the Cox proportional hazards model for these analyses. The outcome variable is time to a first CV event during the study period, and those who do not have an event by the end of follow-up surveillance will be considered as censored. The two branches of this endeavor are (i) the relation of plaque volume and characteristics at one cross-sectional moment in time (such as baseline) to the risk of a subsequent event; and, (ii) the relationship between plaque “velocity”—the rate of change of plaque characteristics over time—to subsequent risk of an event. The velocity and cross-sectional status of plaque are two quite different biological concepts, and it may happen that one or the other alone, and not both, are important. For the first analysis, (i), each patient will have up to two time intervals: baseline to an event or to the 3-year MRI assessment, and then from the 3-year MRI assessment forward to the end of follow-up. By using two intervals per person, one initiated at baseline and the other initiated at 3 years, we will always be using the most recent MRI data on plaque status to compare to subsequent follow-up. This analysis is

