carried out by using time-varying covariates. For the analysis of CV risk in relation to plaque “velocity”, (ii), the methodology is the same, except that each person will have only one interval, from the 3-year MRI scan onward. Independent variables will be the rate of change of plaque characteristics during the first 3 years (e.g., annual % change in lipid composition), as well as the value of plaque variables at the 3-year point, a new “baseline”. For both the baseline and velocity part of these analyses we will attempt to build a multivariate model(s) that will allow us to characterize the CV risk for a given patient. These models will use not only the MRI variables but currently identified risk factors as well, such as age and gender. Our modeling will also address an important issue: Do the plaque variables, even if statistically significant, really add to the prediction of cardiovascular risk? In other words, are the plaque variables really adding something independent of what is already known about risk? We can address this issue by comparing a Cox proportional hazards model with traditional risk factors only, such as age, gender, and smoking status, to a model that includes these traditional factors and also includes any important plaque variables that have detected. We can use either the change in a pseudo-R² statistic (based on likelihood) or use logistic regression and note the increase in the area under the ROC curve when the plaque variables are added into the model with the traditional risk factors. This comment applies to any analyses where there are traditional (known) risk factors available. While statistical significance of a plaque variable may help us to understand the biology better, it is also helpful to know if the use of plaque variables notably increases the prediction of CV events for individuals.

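### The rule for the analysed artery region (D.3) omits the 3-year scan that the main analyses use, and event model (i) in F.3.4 does not always use the most recent MRI

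*Combined protocol and SAP*

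**What the plan says.** **Scans and their measurement.** A.1 Aim 1(a) is to "perform carotid CE-MRI scans for all 180 study subjects at baseline, 1, 2, and 3 years". A.2 repeats it: "All patients will undergo MRI examination of both carotid arteries annually for three years, a total of 4 examinations". Aim 4(a) is to "perform quantitative assessment of plaque lipid, volume, and enhancement at all 4 time points", and A.3 says of the primary endpoint: "These measurements will be performed from the MRI scans at four time points blinded to time sequence of MRI examinations". A.2 also allows an optional late scan in the extension, at a median of six years.

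**Region analysed.** The paragraph after Step 4 in D.3 has images analysed once two examinations are complete. It restricts the analysis to the part of each carotid seen on both the baseline and the 2-year scan, and mentions neither the year-1 nor the year-3 scan.

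**Analyses.** F.3.2 and F.3.3 work on the change from baseline to 3 years. F.3.4(ii) uses the 3-year plaque values and the rate of change over the first 3 years.

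**Event model (i).** F.3.4 says "each patient will have up to two time intervals: baseline to an event or to the 3-year MRI assessment", followed by a second interval from the 3-year scan to the end of follow-up. It concludes that "we will always be using the most recent MRI data on plaque status to compare to subsequent follow-up". The analysis is "carried out by using time-varying covariates". Aim 5(b), which this model serves, is to "determine whether plaque characteristics (lipid content, volume and enhancement) at baseline and its change during therapy are statistically associated with cardiovascular events".

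**The concern.** The D.3 rule decides which vessel segment every plaque variable is measured on, including the primary endpoint. A segment chosen because it is visible at baseline and year 2 may be only partly visible at year 3. The 3-year change could then compare different stretches of artery, and part of it would reflect location and not treatment.

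The F.3.4 point is narrower and touches only Aim 5. The procedure and the property claimed for it disagree. An analyst who follows the interval definition fits one Cox model; one who follows the stated property fits another. If current plaque drives risk, relating events in years 1 to 3 to the baseline scan tends to weaken the association.

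**Working it through.** **1. Region rule against the schedule.**

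| Item | Scans (years) | Source |
|---|---|---|
| Planned and measured | 0, 1, 2, 3 | A.1 Aims 1(a) and 4(a); A.2; A.3 |
| Define the analysed region | 0, 2 | D.3 |
| Used for primary and secondary change | 0, 3 | F.3.2, F.3.3 |
| Used in event models | 0, 3 | F.3.4(i) and (ii) |

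Year 3 is in every analysis row and absent from the region row. Overlap of scans 0 and 2 does not imply coverage at scan 3. The documents give no coverage data, so the loss cannot be sized.

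**2. Update times in event model (i).** Scans exist at 0, 1, 2 and 3 years; the covariate is set at 0 and 3. For an event-free subject scanned on schedule, baseline is the latest scan only in year 0–1. In years 1–2 and 2–3 a newer one exists.

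- First 3 years: 2/3 = 67%.
- Mean age of the plaque value in years 0–3: 3/2 = 1.5 years as written; 1/2 = 0.5 years with annual updating.
- Whole follow-up: A.2 gives a mean of 5 years directly after the extension paragraph. Read as total follow-up, 2/5 = 40%. Read as added to the first 3 years, 2/(3 + 5) = 25%.
- Maximum follow-up: 2/11 = 18% if 11 years is the total, or 2/(3 + 11) = 14% if it means 11 further years.
- Late scan at year 6, followed to year 11: (2 + 5)/11 = 64% as written, and 5/11 = 45% even after annual splitting. The word *always* therefore needs changing either way.

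**3. Effect on the hazard ratio (illustration only).** The documents give no within-person correlation of plaque over time. Assume a standardised, stationary plaque value whose current level drives a small effect, a constant event rate, and correlation r^lag, where r is the year-to-year correlation. The log hazard ratio is then multiplied by the mean of r^lag over follow-up. Over a span of L years from a scan that mean is m(L) = (1 − r^L)/(−L ln r). For 5 years in total:

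- two intervals: [3·m(3) + 2·m(2)]/5
- annual updating: [3·m(1) + 2·m(2)]/5

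| Assumed r | Two intervals | Annual | Ratio | Loss |
|---|---|---|---|---|
| 0.95 | 0.936 | 0.965 | 0.970 | 3% |
| 0.8 | 0.760 | 0.860 | 0.883 | 12% |
| 0.5 | 0.469 | 0.649 | 0.722 | 28% |

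For 3 + 5 = 8 years, 5·m(5) replaces 2·m(2) and the divisor is 8. The losses become 2%, 9% and 25%. At r = 1 the loss is 0%.

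**The case against.** **The two-interval model can be run as written.** F.3.4 defines the intervals twice, and the *always* clause is a rationale, not an instruction. This stands. A reader might infer that the event analysis is unexecutable or invalid; the documents do not support that. Only the stated property is false.

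**Two intervals may be deliberate.** Branch (i) concerns plaque at a single moment such as baseline, and Aim 5(b) asks about baseline and change. This also stands, so a justified two-interval model is acceptable. The mention of time-varying covariates does not rescue the claim, because the update times are fixed at 0 and 3 years.

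**The practical effect may be small.** A reader might infer a materially biased hazard ratio. The documents do not show one. Assume 3% events per year, 5 years, 180 subjects and a true hazard ratio of 1.5 per SD. Expected events are 180 × (1 − e^−0.15) ≈ 25, so the standard error of the log hazard ratio is about 1/√25 = 0.20. The differences in the table, times ln 1.5 = 0.405, are 0.012, 0.041 and 0.073, or about 0.06, 0.20 and 0.37 standard errors. Scan measurement error would shrink the gain further.

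**D.3 may be leftover text.** F.3.5 also gives a two-year change as an example, which fits a design with fewer scans, but that is inference. D.3 is still the operative reading rule. Averaging per slice (F.3.1) adjusts for how many slices a subject has, not for which segment they come from.

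**Wider readings.** A reader might infer that the baseline-to-year-3 treatment comparison is itself the wrong analysis, or that the year-3 scans were in fact read on a different segment. Neither follows. The comparison is a legitimate choice, and the text shows only that common coverage is not assured.

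**Conclusion.** Both passages are wrong as written, and both should be corrected.

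The D.3 rule matters more because it reaches the primary endpoint. It omits the year-3 scan on which the 3-year change rests. Its size cannot be stated from the documents.

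The F.3.4 statement is false for 2 of the first 3 years (67%), assuming scans on schedule and no event or censoring. Over mean follow-up the share is 40% or 25%, depending on how the 5-year mean is read. Any bias tends towards a hazard ratio of 1 and is nil if plaque is stable between scans. The percentages lost in the illustration rest wholly on assumed correlations and should not be quoted as estimates for this trial.

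**What to change.** **D.3, settled before images are read.** Replace the references to two examinations and to the 2-year scan. For each artery, define the matched region as the segment covered by all of that subject's available scheduled scans that are to be analysed (baseline and years 1, 2 and 3). Baseline and year 3 must always be included for the 3-year change. Using available scans keeps subjects who missed one. The cost is that the common region may be smaller than one matched on two scans, and its extent will vary with the number of scans a subject has.

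**F.3.4(i).** Start a new interval at each scheduled annual scan (0, 1, 2 and 3 years) and carry the last scan forward if one is missed. Describe the covariate as *the most recent scheduled annual MRI*; this leaves the optional late scan outside the main model, where it can serve in a labelled sensitivity analysis. Keep a separately labelled baseline-only Cox model for Aim 5(b). If two intervals are kept on purpose, delete *always* and give the reason.

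**Cost.** No new scans or subjects: a few sentences and modest programming. Annual updating asks about current and not baseline plaque, so the two models need distinct labels. A carried-forward scan is still an older value.

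### The velocity term in F.3.4(ii) is conditional on the year-3 plaque value, so on its own it does not answer Aim 5(b), which asks about baseline and change

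*Combined protocol and SAP*

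**What the plan says.** Aim 5(b) in A.1, repeated in A.2 for the extension of up to 11 more years, is to "determine whether plaque characteristics (lipid content, volume and enhancement) at baseline and its change during therapy are statistically associated with cardiovascular events".

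F.3, item 4, splits this work in two. Branch (i) relates plaque status to later events through time-varying covariates, using the baseline scan up to year 3 and the 3-year scan afterwards. Branch (ii) concerns velocity, that is "the rate of change of plaque characteristics over time—to subsequent risk of an event". In branch (ii) "each person will have only one interval, from the 3-year MRI scan onward". The first covariate is described as "the rate of change of plaque characteristics during the first 3 years (e.g., annual % change in lipid composition"). The second plaque covariate in the same model is introduced by the words "as well as the value of plaque variables at the 3-year point"; the plan regards that year-3 value as a fresh baseline. The year-0 value is not listed.

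On interpretation, the plan says that "The velocity and cross-sectional status of plaque are two quite different biological concepts" and that "it may happen that one or the other alone, and not both, are important". It does not say that the velocity coefficient is conditional on the end value. Nor does it say whether the rate is absolute or relative, or whether it uses two scans or four.

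**The concern.** The year-3 value precedes the follow-up in branch (ii), but it is also the end point of the change being studied. Two patients with the same year-3 value can differ in velocity only because they started from different baselines. The velocity coefficient therefore compares a patient who rose to that level with one who was already there.

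Aim 5(b) is naturally read as a different comparison: two patients with the same baseline, one of whom progresses. Neither branch reports that effect. Branch (i) drops the baseline value once the 3-year scan exists, and branch (ii) conditions on the year-3 value. If the branch (ii) coefficient is taken as the answer to Aim 5(b), the trial could report that plaque change is unrelated to events, or even protective, when progression from a given baseline raises risk.

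**Working it through.** The plan gives no figure for this analysis, so there is none to reproduce. It also gives no event rate or hazard ratio for it; all simulation inputs below are assumptions.

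**1. Identity.** Let Y0 and Y3 be the plaque value at baseline and year 3, and V = (Y3 − Y0)/3. The planned linear predictor is

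b1·V + b2·Y3 = (−b1/3)·Y0 + (b2 + b1/3)·Y3.

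So b1 is −3 times the coefficient of Y0 given Y3. Substituting Y3 = Y0 + 3V gives the baseline-adjusted form:

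b1·V + b2·Y3 = (b1 + 3·b2)·V + b2·Y0.

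The effect of change at fixed baseline is therefore b1 + 3·b2 per unit of annual rate, or b1/3 + b2 per unit of total 3-year change.

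**2. Expected values.** Let the true log hazard be a0·Y0 + a3·Y3. Then V given Y3 has coefficient −3·a0, and V given Y0 has coefficient 3·a3.

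**3. Cox check.** Assumed: n = 10,000, SD of Y = 1, correlation of Y0 and Y3 = 0.7, no measurement error, 1,792 to 1,984 events.

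| True log hazard | V given Y3: expected | fitted (z) | V given Y0: expected | fitted (z) |
|---|---|---|---|---|
| 0.5·Y3 (current level) | 0 | 0.076 (0.8) | 1.50 | 1.596 (16.1) |
| 0.25·Y0 + 0.25·Y3 (cumulative level) | −0.75 | −0.865 (−9.2) | 0.75 | 0.681 (7.2) |
| −0.3·Y0 + 0.6·Y3 (extra velocity effect) | 0.90 | 0.952 (9.5) | 1.80 | 1.707 (17.0) |

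Row 2 illustrates the identities. The fitted Y0 coefficient given Y3 is 0.288, and −3 × 0.288 = −0.864, which agrees with −0.865 to rounding. The fitted b2 is 0.515, so −0.865/3 + 0.515 = 0.227, which equals the fitted Y3 coefficient given Y0; 3 × 0.227 = 0.681.

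Within each row the two models have the same log-likelihood (−16060.13, −16911.26 and −15346.27). Fit and prediction are the same; only the meaning of the coefficient differs.

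**4. Other definitions of the rate.** For rows 1 and 2, with the year-3 value in the model:

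- Four-scan slope: 0.067 (z 0.7) and −0.847 (z −9.0). The slope is almost a function of Y0 and Y3 (R² 0.99, or 0.96 with error SD 0.4), assuming that the year-1 and year-2 values scatter around a straight line with SD 0.2.
- Relative % change per year: z 1.1 and −8.8. Here the identity is not exact, but at a fixed positive Y3 the rate (Y3/Y0 − 1)/3 still falls as Y0 rises.
- Two-point absolute change with measurement-error SD 0.4: −0.068 (z −0.9) and −0.779 (z −9.7).

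**5. Trial size.** Assumed: n = 180, about 50 events, 5 years of follow-up from year 3, hazard ratio 1.5–2.0 per SD of plaque, correlation of true levels 0.6–0.8, reading reliability 0.85–0.95, 400 simulated trials per setting. Hazard ratios are per SD of velocity.

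| Risk follows | Given Y3 (% significant) | Given Y0 |
|---|---|---|
| Current level | 0.89–1.00 (4–11%) | 1.27–1.87 (35–97% significant) |
| Average of Y0 and Y3 | 0.72–0.88 (16–54%, mostly in the protective direction) | 1.15–1.39 |

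A second simulation with about 54 events fell inside these ranges: 0.92–0.99 against 1.56–1.59, and 0.76–0.79 against 1.28–1.29.

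**The case against.** The strongest defence is that the model answers a question the plan really asks. F.3, item 4, wants to separate velocity from status, and testing velocity given status at a 3-year landmark does that. If only current level drives risk, a null velocity term is the right answer to that question, and the 4–11% significance rate is at or near the nominal 5%. When velocity truly adds risk, the model finds it with the right sign (row 3, z 9.5). All of this stands.

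Replacing the year-3 value by the baseline value would also have a mirror-image limit: the velocity coefficient is then 3 times the coefficient of Y3 given Y0. When current level alone matters, that term is significant in 35–97% of the simulated trials, so it cannot tell velocity from status. This stands too, and it rules out a simple swap of covariates.

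A reader might infer that the model is invalid, that it leaves baseline out, or that its velocity term is nothing but baseline with the sign reversed. The documents do not support that. For a two-point absolute rate, Y0 is already in the model through V. The exact −3 identity holds only for that definition, and the plan leaves the rate undefined. Aim 5 is also neither the primary hypothesis nor the primary endpoint, and the plan describes this modelling as an attempt to build models rather than as one fixed model.

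The defence does not reach Aim 5(b). That aim names baseline and change, and nothing in F.3, item 4, tells the analyst that the branch (ii) coefficient answers a narrower question.

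**Conclusion.** The point holds as a gap between aim and estimate. The year-3-adjusted velocity term is valid for the question of whether past change adds risk beyond current status. It does not by itself answer Aim 5(b): it is expected to be about null if risk follows current level, and negative if risk follows cumulative level, although progression from a given baseline raises risk in both cases.

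The algebra is exact for a two-point absolute change and needs no assumption about event rates. For a four-scan slope it is approximate; for relative change only the direction of the dependence on baseline carries over. The simulated sizes rest on assumed event counts, hazard ratios, correlations and reliabilities. Which pattern would appear in this trial depends on a true hazard that the documents cannot reveal.

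Severity is moderate. It does not require the model to be replaced, because the missing effect can be added at almost no cost.

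**What to change.** In F.3, item 4, analysis (ii):

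1. Keep the velocity-plus-year-3 model and label its velocity coefficient as the effect of past change beyond current status.
2. For Aim 5(b), also report the effect of change adjusted for the year-0 value. Fit V + Y0 or, for a two-point absolute rate, report the equivalent contrast b1/3 + b2 from the existing model with its confidence interval. State that this term cannot separate velocity from current status.
3. Define the rate: absolute or relative, two scans or four. Because plaque composition is itself a percentage (D.3, item 3(c)), say whether an annual % change means percentage points or relative change.
4. State that no conclusion that plaque change is unrelated to events, or protective, will be drawn from the year-3-adjusted coefficient alone.

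Dropping the year-3 value without adding the baseline value is not a remedy. In the cumulative-level case of the large simulation, velocity alone gave −0.105 (z −1.2).

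The cost is SAP wording and one more reported estimate in a secondary analysis. No new data are needed.
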